10.0 Interim Analyses

Not applicable. There is no interim analysis planned for this study.

11.0 Data Review

Beyond the data screening built into the PRA Data Management Plan, the PRA programming of analysis datasets, tables, figures, and listings (TFLs) provides additional data screening. Presumed data issues will be output into SAS logs identified by the word "Problem" and extracted from the logs by a SAS macro and sent to Data Management.

Review of a pre-freeze TFL run on clean subjects and a post-freeze TFL run on the frozen database allow for further data screening prior to lock. The post-freeze TFL will be discussed with the Sponsor in a data review meeting to identify any final data issues and seek corrections prior to database lock. The PRA Lead Biostatistician and the Sponsor must approve database lock.

12.0 Statistical Methods

In general, continuous variables will be summarized by number of subjects, mean, standard deviation, median, 25th percentile (Q1), 75th percentile (Q3), minimum, and maximum. The mean will be presented to one more and the standard deviation to 2 more decimal places than the precision of the variable, while the quantiles will be presented at the same precision as the original variable. Categorical variables will be summarized by frequency counts and percentages. Percentages will be presented to one decimal place.

For the primary and secondary efficacy endpoints, estimates of proportions and odds ratios will be presented with 95% two-sided confidence intervals. P-values, where required, will be based on a one-tailed test of superiority at an alpha of 0.025.

All TFLs will be presented by study treatment group. All analyses will be performed using SAS version 9.4 or higher.

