10.0 STATISTICAL CONSIDERATIONS

The Phase 3, open-label study is designed to assess the effects of sipuleucel-T in subjects on AS. Subjects will be randomized 2:1 to either a sipuleucel-T arm (investigational arm) or a control arm, stratified by the ISUP Grade Group 1 or 2 and the number of biopsies showing the presence of disease prior to registration. Data will be analyzed by arm under the intent-to-treat (ITT) principle. Generally statistical tests will be performed at the 2-sided 0.05 significance level unless otherwise noted.

The phrases 'statistical analysis' or 'analysis' will be used to mean inferential analysis (such as performing tests of significance, reporting p-values and confidence intervals). When no inferential analysis will be performed, the phrases 'descriptive analysis' or 'descriptive statistics' will be used (for instance, producing summary tables of means, standard deviations, percentages of responders).

Statistical analysis will be done by the sponsor or under the authority of the sponsor. A general description of the statistical methods to be used to analyze the efficacy and safety data is outlined below. Details will be provided in the Statistical Analysis Plan (SAP).

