10.3 Efficacy Analysis

The phrases ‘statistical analysis’ or ‘analysis’ will be used to mean inferential analysis (such as performing tests of significance, reporting p-values and confidence intervals). When no inferential analysis will be performed, the phrases ‘descriptive analysis’ or ‘descriptive statistics’ will be used (for instance, producing summary tables of means, standard deviations, percentages of responders). All efficacy analyses will be conducted on the ITT population and the per protocol population.

Unless otherwise specified, the statistical tests are based on the superiority hypothesis using a one-sided p-value of 0.025 (equivalent to two-sided 0.05 with a result in the hypothesized direction). The final analysis will be performed after all subjects have completed the 36 month biopsy, or have histopathologic upgrade or have withdrawn from the study.

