10.5.2 Secondary Endpoints

The subsequent prostate cancer treatment, if any, for each subject will be determined. The category of subsequent prostate cancer treatment will be identified (e.g., surgery, radiation, androgen deprivation therapy). Subjects initiating alternative intervention will be regarded as sipuleucel-T treatment failures. These data will be summarized descriptively and compared between study arms using the Cochran-Mantel-Haenszel test.

Quality of life data will be summarized descriptively and compared between study treatment arms and in the aggregate within the efficacy population.

Safety data will be summarized descriptively by study treatment arms and in the aggregate within the safety population.

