5.2 Secondary Objectives

- To assess the differential receipt of local or systemic therapy (surgery, radiation, androgen deprivation therapy (ADT)) in each study arm, and the reasons for receipt of further local or systemic therapy
- To assess differences in quality of life (i.e., patient-reported outcomes (PROs)) between sipuleucel-T and control arms
- To evaluate the safety of sipuleucel-T in men with low to intermediate risk localized prostate cancer

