7.2 Secondary Endpoints

7.2.1 Efficacy

Per the protocol, the secondary efficacy endpoints are:

- To determine the number of subjects with subsequent prostate cancer treatment (e.g., surgery, radiation, ADT) in each study arm
- Characterization of PROs by Memorial Anxiety Scale for Prostate Cancer (MAX-PC), Short Form 12 Health Survey (SF-12), The Expanded Prostate Cancer Index Composite for Clinical Practice (EPIC-CP), and International Prostate Symptom Score (IPSS) at baseline and 12-, 24-, and 36-month visits after randomization

The interpretations of these secondary efficacy endpoints based on the objectives, as assessed from baseline at the 12, 24, and 36 months visits post randomization, are as follows:

- Subsequent Prostate Cancer Treatment
 - Proportions of subjects with subsequent prostate cancer treatment
 - Time to the First Subsequent Prostate Cancer Treatment
- Patient Reported Outcomes (PROs). Will assess PROs at each collection point including change from baseline in the
 - MAX-PC total score and subscores for Prostate Cancer Anxiety, PSA Anxiety, and Fear of Recurrence,
 - SF-12 domain and QOL score and the SF-6D Quality adjusted Life Years index
 - EPIC-CP overall response and individual and pooled domain scores, and
 - I-PSS total scores, each of the urinary symptoms scores, and the quality of life due to urinary symptoms score.

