12.6.2.2 PROs

For each PRO total score and pooled domain score or sub-score defined in [Section 8.1.3](#), actual values at baseline and change from baseline at 12, 24, and 36 months visits post randomization will be summarized in the ITT and PP analysis sets in each treatment arm. The best change within 36 months post-baseline will be summarized and compared between the arms. The responses to individual question items will not be summarized except for the EPIC-CP overall urinary function question, which will be presented at baseline and its shift change presented at post-randomization.

To assess potential missing individual items in each PRO questionnaire, a sensitivity analysis in the ITT analysis set will be conducted to calculate total scores and pooled domain scores by summing up all available individual items regardless of any missing individual score.

PRO results will be provided in a listing.

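### The one-tailed superiority rule, with best change as the only between-arm PRO comparison, leaves no way to state a worsening of quality of life inferentially

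*SAP*

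**What the plan says.** - **Rule for p-values.** SAP 12.0, in its paragraph on the primary and secondary efficacy endpoints: "P-values, where required, will be based on a one-tailed test of superiority at an alpha of 0.025". The same paragraph provides two-sided 95% confidence intervals, but names only proportions and odds ratios.
- **PROs fall under it.** SAP 7.2.1 opens its list with "Per the protocol, the secondary efficacy endpoints are" and includes MAX-PC, SF-12, EPIC-CP and IPSS.
- **Objective.** SAP 5.2, matching Protocol 3.2: "To assess differences in quality of life (i.e., patient-reported outcomes (PROs)) between sipuleucel-T and control arms". No direction is given.
- **PRO analysis.** SAP 12.6.2.2 describes by-arm summaries ("change from baseline at 12, 24, and 36 months visits post randomization will be summarized in the ITT and PP analysis sets in each treatment"). Its one between-arm step is: "The best change within 36 months post-baseline will be summarized and compared between the arms". SAP 8.1.3 defines that quantity as the largest change in the favorable direction at any assessment within 36 months. No test, model or interval is named. Protocol 10.5.2 is equally open: "Quality of life data will be summarized descriptively and compared between study treatment arms".
- **Protocol on sidedness.** Protocol 10.0: "Generally statistical tests will be performed at the 2-sided 0.05 significance level unless otherwise noted". Protocol 10.3 sets superiority testing as the default for efficacy, "using a one-sided p-value of 0.025 (equivalent to two-sided 0.05 with a result in the hypothesized direction").

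**The concern.** A one-tailed superiority test asks only whether sipuleucel-T is better. That suits the primary endpoint. It does not suit an objective with no direction, in an open-label trial where only one arm undergoes leukapheresis and infusion and the comparator is surveillance alone. The choice of best change points the same way, because it keeps each man's most favorable visit and discards the others. With no interval for a mean difference, nothing in the PRO plan produces an inferential statement about harm. A real deterioration would be reported as no evidence of superiority, with the by-arm means left for the reader to interpret.

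**Working it through.** **1. The plan's own figure.** Inputs from SAP 6.2: success 0.70 versus 0.84, 2:1 allocation, one-sided 0.025, 300 + 150 men, at least 90% power.
- Odds ratio = (0.84/0.16)/(0.70/0.30) = 2.25, as stated.
- The continuity-corrected formula for 90% power needs 149 controls, 447 in total. The uncorrected formula needs 417 and gives 92.1% power at 450.
- Exact enumeration of a one-sided Fisher test at 150/300 gives 90.3%.

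The stated size and power reproduce. The documents give no power or effect size for any PRO.

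**2. Detecting a worsening by a simple comparison of means.** Effects are in SD units and are assumed.
- SE with full data = sqrt(1/300 + 1/150) = 0.100 SD.
- SE with 20% missing (assumed; 240 versus 120) = sqrt(1/240 + 1/120) = 0.112 SD.
- Two-sided 0.05 power to declare worsening d = Φ(d/SE − 1.96). For d = 0.3: Φ(3.00 − 1.96) = 85% with full data; Φ(2.68 − 1.96) = 77% with 20% missing.
- One-tailed rule: the only possible rejection is for benefit, with probability Φ(−d/SE − 1.96). For d = 0.3 and full data this is 3.5 × 10⁻⁷.

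| True worsening (SD) | Two-sided, 300 v 150 | Two-sided, 240 v 120 |
|---|---|---|
| 0.1 | 17% | 14% |
| 0.2 | 52% | 43% |
| 0.3 | 85% | 77% |
| 0.4 | 98% | 95% |
| 0.5 | 99.9% | 99% |

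An observed z of −3 gives a one-sided p of 0.9987 and a two-sided p of 0.0027.

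**3. Effect on claims of benefit.** The critical value is 1.96 under both one-sided 0.025 and two-sided 0.05, so power to declare benefit is identical.

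**4. Sidedness is only half the problem.** Simulation of best change over three visits: 300 versus 150, SD 1, between-visit correlation 0.4 to 0.8 (all assumed), 3,000 trials per setting, two-sided test.

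| 0.3 SD worsening | Found by best change | Found by month-12 difference |
|---|---|---|
| Month 12 only | 13–16% | about 85% |
| All three visits | 88–94% | 85–86% |

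Best change does well for a sustained worsening and badly for a temporary one.

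**The case against.** - **No PRO test is named.** P-values apply only where required, SAP 12.6.2.2 specifies none for PROs, and SAP 12.6.1.2 makes the primary test alone decisive. This stands. The gap is the absence of any route to an inferential statement, and trial success is not at stake.
- **The SAP follows the protocol.** A reader might infer from Protocol 10.0 that the SAP departs from a two-sided protocol rule. The documents do not support that. Protocol 10.0 allows exceptions and Protocol 10.3 makes one for efficacy. But 10.3 is itself a default that can be overridden, so the SAP is free to specify two-sided PRO tests.
- **Harm would remain visible.** A reader might also infer that the plan conceals a worsening. It does not. SAP 12.0 and 12.6.2.2 require by-arm summaries of change at each annual visit, including means and SDs, from which an approximate difference and interval can be computed. What is missing is a prespecified one.
- **Procedural burden is over before the first PRO visit.** First leukapheresis within 60 days, infusion about 3 days later and two further infusions at about 2-week intervals put the last infusion near day 60 + 3 + 28 = 91. The first on-study PRO is at month 12. This stands: no PRO test would capture acute burden, which the adverse-event analyses cover. The point concerns later differences.
- **Multiplicity grows.** Type I error per PRO test rises from 0.025 in one direction to 0.05 over both. Counting MAX-PC (4 scores), SF-12 with SF-6D (8 + 2 + 1 = 11), EPIC-CP (6) and the I-PSS total (1) gives 22 scores, and 22 × 3 visits = 66 comparisons. With no true differences, about 66 × 0.025 = 1.65 would be nominally significant in each direction. This is why the results should be labelled non-confirmatory and led by the intervals.
- **Subsequent treatment is less exposed.** SAP 12.6.2.1 already gives exact intervals for each arm's proportion and Kaplan-Meier estimates. This stands, and the point is confined to PROs.

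**Conclusion.** The point holds as a cheap improvement. As written, the PRO plan can support an inferential statement of benefit but not of worsening, for two reasons that reinforce each other: the one-tailed rule, and a single between-arm comparison built from each man's most favorable visit. The objective asks about both directions. For an assumed 0.3 SD worsening, a simple two-sided comparison of means has 85% power with full data and about 77% with 20% missing. Under the SAP rule a worsening cannot be the conclusion at any effect size. The 85% rests on assumed effect sizes and a by-visit comparison that the SAP does not now plan, so it measures what the trial could learn and is not the loss from sidedness alone. Making the best-change comparison two-sided would still miss most worsenings confined to one visit. The primary analysis is unaffected.

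**What to change.** 1. In SAP 12.0, limit the one-sided 0.025 rule to the primary endpoint.
2. In SAP 12.6.2.2, report for each PRO score the between-arm mean difference in change from baseline at 12, 24 and 36 months, with a two-sided 95% CI and a two-sided 0.05 p-value. Label these non-confirmatory and unadjusted for multiplicity. Best change may stay as a supplementary summary, but not as the only comparison.
3. Reconcile Protocol 10.0, Protocol 10.3 and SAP 12.0 so that one statement says which tests are one-sided.

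The cost is a few sentences and a difference-and-interval column in the PRO tables, with no new data. The price is the wider type I error per PRO test described above. The threshold for declaring benefit, the primary test and N = 450 stay as they are.

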12.1 Subject Population

The number and percentage of subjects in each analysis set defined in [Section 9.0](#) will be presented overall and by study treatment arm. A by-subject listing of analysis set will be provided.

12.2 Disposition

The numbers and percentages of subjects screened, randomized and treated in the study will be presented, together with the number and percentage of subjects who terminated the study treatment prematurely and a breakdown of the corresponding reasons for termination of study drug, and the number and percentage of subjects who withdrew from the study prematurely and a breakdown of the corresponding reasons for study withdrawal. These will be presented overall and by study treatment arm. Subjects who discontinued from the study will be listed.

12.3 Important Protocol Deviations

Per PRA processes, important protocol deviations data will be entered into the Clinical Trials Management System (CTMS). The study team and the Sponsor will conduct on-going reviews of the protocol deviation data from CTMS and the resulting set of evaluable subjects throughout the study, adjusting the deviation criteria as appropriate. The subjects in the per protocol population must be finalized at the post-freeze data review meeting (or earlier), prior to database lock. Criteria for designation of a protocol deviation as important can found in the study's Protocol Deviations and Violations document, under the Guidance tab.

Important protocol deviations for subjects in the ITT population will be summarized by deviation category, overall and by study treatment arm. Important protocol deviations will also be listed.

12.4 Treatments

12.4.1 Extent of Study Drug Exposure

Exposure to leukapheresis and sipuleucel-T will be summarized in the ITT Population among the subjects randomized to sipuleucel-T. Number of reported leukapheresis, number of reported infusions, subjects reporting at least 1 leukapheresis, a CVC line, at least 1 infusion, and subjects who received 3 infusions and underwent only 3 leukapheresis will be summarized. The number and percentage of subjects with at least 1 dose interruption will be presented.

A listing of sipuleucel-T exposure will also be created. This data can be found on the Sipuleucel-T - IV/Infusion Administration CRF pages.

12.4.2 Concomitant Medications

Medications received concomitantly with study drug will be coded using World Health Organization (WHO) Drug Enhanced (version: March 2016) and categorized by Anatomical Therapeutic Chemical (ATC) Classification. Concomitant medications will be summarized by ATC code and drug name by study treatment received in the Safety population. A listing of concomitant medications will also be created.

12.5 Demographic and Baseline Characteristics

The demographic and baseline characteristics variables will be summarized in the ITT population overall and by study treatment arm.

The demographic variables include age (years), ethnicity, race, weight (kg), height (cm), smoking history, and Eastern Cooperative Oncology Group (ECOG) status.

The baseline characteristics include:

- Medical history, including abnormal ECGs and DREs (coded by MedDRA dictionary version 18.0 or higher and summarized by system organ class (SOC) and preferred term (PT));
- Abnormal physical examination findings
- Cardiovascular event risk factors
- ISUP grade group
- PSA
- Testosterone
- Viral Serology

Listings of the demographic and baseline characteristics will also be presented.

12.6 Efficacy Analyses

12.6.1 Primary Endpoint

The counts and proportions of subjects without ISUP Gleason group upgrade within 36 months of randomization will be presented by study treatment arm and overall. Exact 95% confidence intervals (CIs) for the proportions and the odds of no upgrade will also be presented. The reasons for failure (upgrade within 36 months) will be summarized as well. The exact Cochran-Mantel-Haenszel test of the null hypothesis of no difference in the odds of no ISUP grade group upgrade across treatment arms, while accounting for stratification by baseline ISUP grade group and number of biopsies, will be performed in the ITT analysis set.

12.6.1.1 Methods for Handling Dropouts and Missing Data

Missing baseline or post-baseline ISUP grade group will result in imputed failure status as defined in [Section 8.1.1](#). These methods allow for a conservative estimate of the proportion that do not have ISUP grade group upgrade if information is not available to determine no upgrade. The pattern of missingness across study treatment arms will be explored using a Kaplan-Meier plot of missing ISUP grade group assessments across time.

12.6.1.2 Multiplicity

Not applicable. There is one test of the primary endpoint that defines the success or failure of the study.

12.6.1.3 Sensitivity Analyses

To evaluate the impact of the potential asymmetric drop-outs, the exact Cochran-Mantel-Haenszel test of the null hypothesis of no difference in the odds of no ISUP grade group upgrade across treatment arms, while accounting for stratification by baseline ISUP grade group and number of biopsies, will be repeated in the per protocol analysis set as a sensitivity analysis.

In a separate sensitivity analysis, the last observation carried forward method will be applied to the primary endpoint in the ITT analysis set. In other words, all subjects with non-missing ISUP grade group at baseline and without any upgrading within 36 months after randomization (even without any post-randomization ISUP grade group) will be counted as successes in the primary efficacy endpoint. Subjects upgrading before 36 months, those with an upgrade at Biopsy 2, or those with missing ISUP grade group at baseline will be counted as failures.

Three sipuleucel-T subjects were replaced pursuant to protocol section 6.4. Sensitivity analyses will be conducted to evaluate the impact, if any, of the inclusion of these subjects in the analysis of the primary and secondary endpoints.

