6.3.2 Discontinuation from Study Participation

A subject in either the sipuleucel-T or control study arms will end study participation, including discontinuation of sipuleucel-T (sipuleucel-T arm only), biopsy and blood sample collection, for any of the following reasons:

- The subject withdraws consent or loses the ability to provide informed consent to participate in the study for any reason
- The subject is diagnosed with locally advanced or metastatic prostate cancer
- The subject dies or is lost to follow-up ([Section 6.5](#))

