6.7 Restricted Therapies During Sipuleucel-T Treatment Period

Certain therapies and procedures could confound the results of this study. Therefore, subjects who are randomized to the sipuleucel-T arm and receive any of the following, 30 days prior to the first infusion until 30 days after the last infusion, will discontinue sipuleucel-T treatment (Section 6.3.1):

- Any immunosuppressive therapy, including systemic steroids. Use of inhaled, intra-nasal, intra-articular, and topical steroids is allowed. Oral or IV steroids to prevent or treat IV contrast reactions are allowed
- Blood products
- GM-CSF or G-CSF
- Any vaccinations

Subjects that discontinue sipuleucel-T treatment and have received > 0 mL of sipuleucel-T will remain in the Active Phase and follow the schedule of events (Table 1).

6.8 Restricted Therapies from Randomization to End of Active Phase (Sipuleucel-T and Control Arms)

Certain therapies and procedures could confound the results of this study. Therefore, subjects who receive any of the following will go from Active Phase of the study to the Follow-up Phase of the study:

- Any local or systemic therapy or procedures for prostate cancer (e.g., ADT, radical prostatectomy, external beam radiation or brachytherapy)
- Any local or systemic therapy or procedure targeting the prostate (e.g., transurethral resection of the prostate (TURP) or 5-alpha reductase inhibitor)
- Major surgery at the discretion of the sponsor's Medical Monitor
- Any investigational product for prostate cancer or other condition (per sponsor's Medical Monitor approval)
- Any other therapy at the discretion of the sponsor's Medical Monitor

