A subject has a Gleason group upgrade if they had an ISUP Grade Group 1 at baseline and an ISUP Grade Group 2 or higher within 36 months post-randomization or if they had an ISUP grade group 2 at baseline and an ISUP Grade Group 3 or higher within 36 months post-randomization. The primary endpoint is the proportion of subjects in the treatment arm without ISUP Gleason group upgrade within 36 months of randomization. That is, success for this endpoint is defined as not having a Gleason group upgrade at Biopsy 1 or Biopsy 2, after being assessed at least through 36 months (Biopsy 2). Subjects upgrading before 36 months, those with an upgrade at Biopsy 2, or those with missing ISUP grade group at baseline or Biopsy 2 will be counted as failures.

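### The SAP's last-observation-carried-forward sensitivity analysis scores as 36-month successes, where no central-review upgrade is on file, men never re-biopsied, men treated for prostate cancer and men removed for locally advanced or metastatic disease

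*SAP*

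**What the plan says.** **Sensitivity rule.** SAP 12.6.1.3 gives success to "all subjects with non-missing ISUP grade group at baseline and without any upgrading within 36 months after randomization", and extends this to men "even without any post-randomization ISUP grade group) will be counted as successes in the primary efficacy endpoint". The failure list has three entries: an upgrade earlier than month 36, an upgrade found at Biopsy 2, and no baseline grade. Prostate cancer therapy, locally advanced or metastatic disease, and death are not on it.

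**Primary rule.** SAP 8.1.1 treats missing grades the opposite way: "those with missing ISUP grade group at baseline or Biopsy 2 will be counted as failures".

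**Why a man may have no later grade.**
- Protocol 6.8: "subjects who receive any of the following will go from Active Phase of the study to the Follow-up Phase of the study". The first item listed is "Any local or systemic therapy or procedures for prostate cancer (e.g., ADT, radical prostatectomy, external beam radiation or brachytherapy". The Follow-up Phase has no scheduled biopsy.
- Protocol 6.3.2 ends participation, biopsies included, when "The subject is diagnosed with locally advanced or metastatic prostate cancer".
- Protocol 6.3.1 withdraws from the study a sipuleucel-T man who declines his first infusion or the leukapheresis for it.

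**Related statement.** On subsequent treatment, Protocol 10.5.2 says: "Subjects initiating alternative intervention will be regarded as sipuleucel-T treatment failures".

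**The concern.** For a man with no post-randomization biopsy, the value carried forward is the grade that made him eligible. That grade cannot be an upgrade over itself, so his success is automatic and is not evidence about month 36. Both documents otherwise define success as having been assessed through Biopsy 2 (Protocol 10.5.1, SAP 8.1.1).

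For a man removed because advanced disease was found, the rule goes further. Known progression is recorded as a 36-month success if no upgrade had been graded first.

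This is the only planned analysis that handles missing grades differently in the full ITT set. The per-protocol repeat drops men without a month-36 grade and requires three infusions in one arm only. The analysis of replaced men tests whether to include them, not what to impute. If the share of unassessed men differs by arm, the rule favours the arm with more of them.

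**Working it through.** **Inputs.** SAP 6.2: success 0.70 in control and 0.84 under sipuleucel-T, 150 and 300 men, one-sided alpha 0.025, power at least 90%. No dropout or treatment rate is given, so the unassessed shares below are assumptions.

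**Step 1: the plan's own figure.** Odds ratio = (0.84/0.16)/(0.70/0.30) = 2.25, as stated. Pooled success = (150×0.70 + 300×0.84)/450 = 0.793. Null standard error = √(0.793×0.207×(1/150+1/300)) = 0.0405. Alternative standard error = √(0.21/150 + 0.1344/300) = 0.0430. Power = Φ((0.14 − 1.96×0.0405)/0.0430) = 92.1%. Fisher's exact test gives 90.3%. The stated power reproduces. It makes no allowance for unassessed men.

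**Step 2: who becomes a success.** Each row supposes a baseline grade and no recorded central-review upgrade.

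| Man | Primary analysis | LOCF analysis |
|---|---|---|
| Clean Biopsy 1, no Biopsy 2 grade | failure | success |
| Never re-biopsied | failure | success |
| Treated for prostate cancer, no Biopsy 2 grade | failure | success |
| Removed for locally advanced or metastatic disease | failure | success |

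The one-arm withdrawal route feeds the second row. SAP 12.6.1.3 reports three replaced sipuleucel-T men. They received no product (SAP 9.1.1) and stay in the ITT set (SAP 9.1). Unless an upgrade was recorded, each is an LOCF success: 3/300 = 1.0 point of that arm's rate.

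**Step 3: size under no true effect.** Let m be the share with no Biopsy 2 grade and no recorded upgrade, and let 70% of the others succeed in both arms. Then LOCF success = 0.70(1 − m) + m, and missing-as-failure success = 0.70(1 − m). Differences are sipuleucel-T minus control, in percentage points.

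| m, sipuleucel-T / control | LOCF rates | LOCF difference | Missing-as-failure difference | LOCF one-sided p < 0.025 favouring sipuleucel-T |
|---|---|---|---|---|
| 10% / 3% | 73.0% / 70.9% | +2.1 | −4.9 | 7.0% |
| 20% / 10% | 76.0% / 73.0% | +3.0 | −7.0 | 10.5% |
| 20% / 5% | 76.0% / 71.5% | +4.5 | −10.5 | 18.1% |
| 10% / 20% | 73.0% / 76.0% | −3.0 | +7.0 | 0.4% |

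The last column uses the pooled normal test at 150 and 300, not the stratified exact test. Example for 20% / 10%: Φ((0.03 − 1.96×0.0433)/0.0438) = 10.5%. These are not error rates of the trial, because this analysis decides nothing.

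**Step 4: what the two ITT analyses cover.** If unassessed men in both arms succeed with one common probability q, the difference is (q − 0.70)(m_S − m_C), where S is sipuleucel-T and C is control. This is linear in q. At 20% / 10% it runs from −7 points (q = 0, the primary rule) to +3 points (q = 1, LOCF). If q may differ by arm, the range is 0.56 − 0.73 = −17 points to 0.76 − 0.63 = +13 points. No planned analysis looks outside −7 to +3.

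**The case against.** The strongest reply is that the two ITT rules are deliberate opposite extremes, so agreement between them is informative. That stands for any success probability shared by the arms (Step 4). A reader might infer that the sensitivity result cannot be interpreted at all; the documents do not support that.

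Second, the endpoint is histologic, and treatment is not evidence of upgrade. Protocol 2.1.1 cites a surveillance cohort in which men stopped surveillance for PSA-doubling time (43.5%) or preference (6%) as well as grade progression (35%). Treatment is also analysed separately (SAP 12.6.2.1). This stands against scoring every treated man as a failure in the only version of this analysis. A reader might take Protocol 10.5.2 to require that score, but its sentence sits in the secondary-endpoint section and does not define the primary endpoint, so the SAP does not contradict it.

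Third, many of these men may have a later grade. Prostatectomy and unscheduled slides go to central review (Protocol 8.11), a biopsy before withdrawal is encouraged (Protocol 6.3), and Protocol 10.5.1 counts upgrades found at prostatectomy. This narrows the groups to men without a recorded upgrade. SAP 8.1.1 does not list prostatectomy tissue among its grade sources, so how far it narrows them is unclear.

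Fourth, a reader might conclude that men never re-biopsied should simply be failures here. Under the null scenarios that gives larger distortions (−4.9 and −10.5 points against +2.1 and +4.5) and nearly repeats the primary analysis.

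The SAP also plans a Kaplan-Meier plot of missing grades (12.6.1.1). It would show an imbalance but not its effect on the result.

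**Conclusion.** The point holds as a defect in one sensitivity analysis. As written, the rule credits three groups with 36-month success when no upgrade was recorded. For men removed with advanced disease, that runs against what is known about them. For men never re-biopsied it rests on the baseline grade alone, and one route into that group exists only in the sipuleucel-T arm.

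The primary test, which SAP 12.6.1.2 says alone decides the study, is unaffected. The distortion under no true effect is 0.30 × (m_S − m_C): +2.1 to +4.5 points in the assumed scenarios with more unassessed sipuleucel-T men, and negative if the imbalance reverses. Against the planned 14-point effect, 4.5 points is about a third. This rests on assumed shares and on unassessed men upgrading at the design's 30%. It is a range of what could happen, not a demonstrated bias. The remaining gap is that no planned analysis lets the missing-grade assumption differ by arm.

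**What to change.** Amend SAP 12.6.1.3 before database lock:

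1. In this analysis, score removal for locally advanced or metastatic prostate cancer before Biopsy 2 as failure, whatever earlier grade is on file.
2. Otherwise carry success forward only from at least one post-randomization central-review grade without upgrade. For men with none, do not fix a single success or failure. Vary their assumed success rate from 0 to 1 separately in each arm, and report where the conclusion changes (a tipping-point analysis).
3. Beside this histology-only version, add one that scores prostate cancer therapy before Biopsy 2 without a central-review upgrade as failure.
4. Tabulate by arm the men in each class: success carried from a post-randomization grade; baseline grade only, with replaced men and those withdrawn for declining the first infusion or leukapheresis shown separately; treated without upgrade; and removed for advanced disease.

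This concerns endpoint scoring only and changes nothing in patient management. The treatment and disposition data are already collected (SAP 8.1.2.1 and 12.2). The cost is SAP wording, slightly more analysis work, and somewhat lower success rates in the sensitivity analysis. The primary analysis stays as it is.
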